10.0 Study Design / Methods

| Schedule of Events | Screening Call | In-Person Baseline Visit ^a | Monthly Call (Months 1,2,4,5,7,8,10,11) After Baseline* | Appointment Reminders (15 Days & 2 Days Before 3, 6, 9 Month Visit)** | Post 3, 6, 9 Month Visit ^a | Appointment Reminders (15 Days & 2 Days Before Post 12 Month Visit) | Post 12 Month Visit ^a |
|--|--|---------------------------------------|---|---|---------------------------------------|---|----------------------------------|
| Participation Assessment | X | | | | | | |
| Informed Consent & HIPAA | | X | | | | | |
| Steps To Care Intake Assessment Form | | X | | | | | |
| Steps To Care Reassessment Form | | | X | | X | | X |
| Participant Completed Assessments: Healthcare Resource Use Survey, Test of Functional Health Literacy | | X | | | | | |
| MacArthur Ladder, Experiences of Discrimination (EOD) measure | | X | | | | | X |
| LupusPRO | | X | | | X | | X |
| Medication Adherence Diary Review | | X | | | X | | X |
| Participant Completed Assessments: Perceived Stress Survey, Social Support Survey & Modified Picker Survey, Patient-Centered Care Questionnaire | | X | | | | | X |
| Appointment Reminder Calls | | | | X | | X | |
| Patient Satisfaction with Interpersonal Relationship with Navigator (PSN-I) survey | | | | | | | X |
| As Needed | | | | | | | |
| 1 Week F/U Call After Medication Change | Medication changes can occur at any time during the study. Medications to be included are those prescribed for your SLE. | | | | | | |

*Monthly Call window = +/- 7 calendar days.

**Appointment Reminder window = +/- 2 business days.

α All in person visits can be done in clinic or remotely via doxy.me

Screening:

PN will assess patient willingness to participate in the study as well as eligibility via a phone call, remote visit, in person at their clinic appointment, or once stable during an inpatient hospital stay.

Baseline In Person or Remote Visit:

Upon enrollment (Baseline visit) and signing of informed consent and HIPAA authorization, the PN will provide the following questionnaires, surveys and diaries:

- 1) Steps to Care Intake Assessment Form,
- 2) Healthcare Resource Use Survey,
- 3) LupusPRO survey,
- 4) Test of Functional Health Literacy,
- 5) Medication Adherence Diary,
- 6) Perceived Stress Survey,
- 7) Social Support Survey & Modified Picker Survey Patient-Centered Care Questionnaire,
- 8) Experiences of Discrimination (EOD) measure,

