For the Usual Care Group only: As stated above, in order to properly obtain data, while minimizing risk to patients in this study, the study staff will only utilize data for those patients that have already enrolled in the Division of Rheumatology Core Center for Clinical Research (CCCR; Pro21985). These patients will have provided properly executed HIPAA authorization to utilize Protected Health Information through the CCCR for optional research portions of the CCCR study (see General Comments of IRB application to review CCCR HIPAA Authorization). Data on healthcare utilization and adherence to prescribed medications based on pharmacy records would be collected on the Usual Care group as part of standard quality of care monitoring, which are allowed to be collected through the CCCR; Pro21985. This data will be provided through a formal request process, reviewed by the executive committee of the CCCR, and provided to this study's staff via this request. Note that this group of patients (Usual Care) will not have a formal informed consent process completed and executed as only analysis of data already collected for standard of care is necessary and falls under the HIPAA Authorization for the CCCR.

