12.0 Data Management

The MUSC CCCR Patient Resource Core (Pro00021985) will act as an honest broker for the provision of clinical data of patients that fit criteria and are already enrolled in the CCCR study. The clinical data provided to the PN and PI of this study will include all data listed in sections 4.0 & 10.0 and will be provided to study staff de-identified. The data provided will only include 25 patient data sets for the "Usual Care" group that has not had contact with the patient navigator and serves as the control group for this study.

Analyses will be primarily descriptive in nature. Means, standard deviations, medians, inter-quartile ranges, and proportions will be reported on each outcome of interest, as appropriate. These statistics will be reported at baseline, 3 months, 6 months, and at 12 months for the primary outcome measure (Medication Adherence) and all secondary outcome measures. The secondary outcome measures are 1) Adherence with Primary Care and Specialty Care Visits, 2) Adherence with Lab and other Study Appointments, 3) Healthcare Utilization, 4) Disease-related Damage, 5) Corticosteroid Use and 6) Patient-Reported Outcomes.

In addition to results reported by our site, we will report results from our collaborating site, University of Alabama at Birmingham (UAB), during their implementation of the LPNP protocol.

Analyses will include estimates of site to site variability utilizing a combined MUSC and UAB dataset. All data sharing will be de-identified and maintained on MUSC's supported REDCap platform. Shared data and analyses were included in the Scope of Work executed by NIH subaward funding of 3P30AR072582-03S1, Improving Minority Health in Rheumatic Diseases.

Although this is not a randomized trial, we will use statistical methods such as propensity score weighting (36) to gain an understanding of how the use of PNs improves outcomes (e.g. medication adherence) when compared to usual care. Generalized linear mixed models will be used in conjunction with propensity score weighting to compare treatment group outcomes and estimate relevant effect sizes while adjusting for relevant baseline covariates (e.g. age, SLEDAI) and accounting for repeated measures within patients over time.

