Since we will have all healthcare utilization data over the 12-month time, calculations will also be performed to indicate how intervention and control patients compared monthly throughout the study. These data will help us design a larger randomized, multi-center, clinical trial. The pilot study will be extremely valuable both in demonstrating feasibility and in providing data for sample size estimation for our next step trial.

Since this is a pilot study, our sample size of n=25 patients in the PN group and n=25 patients in the "Usual Care" group were selected primarily to ensure that we can assess feasibility of providing this intervention in this high-risk population. Having n=25 patients in each group will also allow us to estimate group-specific outcomes with relatively strong precision (i.e. within \pm 0.3 standard deviations for continuous outcomes and \pm 10%-20% percentage points for proportions). All this information will be vital for designing a future, definitive randomized controlled trial. In obtaining preliminary estimates of effectiveness, our sample sizes will also provide sufficient power (>80%) to detect moderate differences in medication adherence rates between treatment groups, assuming 2-sided hypothesis testing and an alpha level of 0.05.

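### Medication adherence, the primary outcome, has no common definition, and its only named sources differ by group (navigator-reviewed diary versus pharmacy records)

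*Combined protocol and SAP*

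**What the plan says.** **Outcome.** Section 4.0 lists improvement in medication adherence without an instrument, although the same sentence names LupusPRO for disease status. Section 12.0 makes adherence the primary outcome: "These statistics will be reported at baseline, 3 months, 6 months, and at 12 months for the primary outcome measure (Medication Adherence"). No section gives a formula, a threshold, a list of drugs to be scored or an observation window.

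**Navigator group.** The Schedule of Events in Section 10.0 has a row "Medication Adherence Diary Review", marked at baseline and at months 3, 6, 9 and 12. The diary is first handed out at the baseline visit, where "the PN will provide the following questionnaires, surveys and diaries". After a medication change the navigator also checks that it has been completed. Table 1 in Section 3.0 lists the diary among the programme's features for encouraging adherence.

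**Usual Care group.** Section 10.0, in a paragraph restricted to this group, says: "Data on healthcare utilization and adherence to prescribed medications based on pharmacy records would be collected on the Usual Care group". That paragraph limits the group to data already gathered in standard care. Section 12.0 then says: "The clinical data provided to the PN and PI of this study will include all data listed in sections 4.0 & 10.0". The same paragraph says that the group "has not had contact with the patient navigator and serves as the control group for this study".

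**Comparison.** Section 12.0 commits to a between-group analysis: "Generalized linear mixed models will be used in conjunction with propensity score weighting to compare treatment group outcomes and estimate relevant effect sizes". It also states that "our sample sizes will also provide sufficient power (>80%) to detect moderate differences in medication adherence rates between treatment groups".

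**The concern.** A group comparison is interpretable only if the outcome means the same thing in both groups. Here the only source named for one group is a self-report diary, supervised by the person delivering the intervention. The only source named for the other is pharmacy records. The first reflects what patients write down, the second what was dispensed. Any systematic gap between them would appear as a navigator effect or would cancel a real one.

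Propensity weighting and covariates such as age and SLEDAI make the patients more alike. They do not make the instruments alike. When every navigator patient is measured one way and every control the other, no patient supplies the information needed to separate source from treatment.

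At stake are the between-group adherence estimate and its use in sizing the next trial. Feasibility and within-group description are not affected.

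**Working it through.** **1. The plan's own figure.** The claim of more than 80% power cannot be reproduced, because the moderate difference is given no number. With 25 per group and two-sided 0.05, a single-time-point t test needs a standardised difference of 0.81 for 80% power. A comparison of rates needs about 33 to 39 points, for an assumed lower rate of 20% to 60%. This is background; the present point does not depend on it. Any such figure does presuppose one outcome variable.

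**2. Is there a common source?**

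| | Navigator group | Usual Care group |
|---|---|---|
| Diary | Sections 3.0 (Table 1) and 10.0 | Not available: no navigator contact, standard-care data only |
| Pharmacy records | Not stated | Section 10.0 |
| Formula, drugs, window | Not stated | Not stated |

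The one sentence that might supply a common source is the Section 12.0 statement covering everything listed in Sections 4.0 and 10.0. Read literally it includes a navigator-issued diary for patients who never met the navigator. It conflicts with the text around it and does not settle the matter.

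**3. What the comparison estimates.** Let τ be the true navigator effect and g the mean gap, diary minus pharmacy records, for the same true adherence.

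- Follow-up contrast, even with perfect weighting: τ + g.
- Change-from-baseline contrast: τ + (g at follow-up − g at baseline). This equals τ only if the gap is constant and each source has a valid pre-navigator value.

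The plan reports adherence at baseline and marks a diary review there. But the diary is first given out at that visit, and no section explains how a pre-navigator value would be obtained.

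**4. Size under stated assumptions.** From the documents: n = 25 per group, two-sided 0.05. Assumed, because the documents give nothing: the diary is used as the outcome, τ = 0, and g is 10, 20 or 30 points.

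*Proportions.* P(reject) = Σ Bin(a; 25, p) · Bin(b; 25, p + g), summed over all pairs (a, b) that the test rejects.

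| Gap | Pooled z, p = 50% | Pooled z, p = 30–60% | Fisher, p = 50% | Fisher, p = 30–60% |
|---|---|---|---|---|
| 0 | 6.5% | – | 3.3% | – |
| 10 | 13% | 12–13% | 8% | 7–8% |
| 20 | 33% | 33–35% | 23% | 23–24% |
| 30 | 64% | 62–73% | 51% | 51–59% |

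*Continuous score.* Noncentral t with 48 degrees of freedom and noncentrality (g/SD)·√(25/2). For g = 20 and SD 25 this is 0.8 × 3.54 = 2.83.

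| Gap | SD 25 | SD 30 |
|---|---|---|
| 10 | 28% | 21% |
| 20 | 79% | 64% |
| 30 | 99% | 93% |

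At SD 25, a gap of 4.7 points already doubles the error rate from 5% to 10%.

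*Masking.* With τ = 20 and SD 25, power is 79% with no gap. It falls to 55% if the navigator-group source reads 5 points low (net 15) and to 28% if it reads 10 points low (net 10).

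**5. Cancellation check.** Simulated change from baseline with SD 25, assumed within-patient correlation 0.5, a constant 20-point gap at both times and τ = 0: rejection is about 5%. Differencing therefore removes a constant gap, but only with the valid baseline that step 3 finds undescribed.

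The figures in step 4 are for unweighted tests at one time point. They show scale and do not give the operating characteristics of the planned weighted mixed model.

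**The case against.** The best reply is that the mismatch is inferred. No sentence makes the diary the outcome measure, and its place in Table 1 suits a process tool at least as well. The Schedule of Events also has no row for disease damage or corticosteroid use, both secondary outcomes, so record-based outcomes may simply be left off it. The Usual Care paragraph deals with authorisation, which would explain why pharmacy records are mentioned only there. Section 12.0 also expects full 12-month utilisation data on both groups. Pharmacy records for everyone is thus a plausible intention.

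That much stands, and it is why the finding is that the comparison can mix instrument with treatment, not that it will. But the intention is nowhere written, and this is the primary outcome.

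A second reply is that the gap sizes are assumed and that a constant gap cancels in a change analysis. Both are true. The second needs a pre-navigator baseline from the same source, which the plan does not describe.

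A third is that this is a pilot, with mainly descriptive analyses and a sample size chosen for feasibility. That leaves the severity open to argument. It does not remove the commitment to a modelled adherence comparison, the power statement, or the intended use of the data for sample-size estimation.

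Finally, a shared pharmacy source can carry its own bias: Table 1 has the navigator help patients enrol in medication assistance programmes, and those supplies may be missing from pharmacy records, mainly in the navigator group. This is a fair caution, and the remedy has to address it.

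**Conclusion.** The concern holds. The primary outcome has no definition common to both groups, and using the sources as written ties instrument completely to group. Under assumed gaps of 10 to 30 points and no true effect, the chance of a significant single-time-point result is roughly 7–73% for proportions (bases 30–60%, Fisher or pooled z) and 21–99% for a continuous score (SD 25–30). An opposite gap can hide a real effect just as readily. These figures rest on the diary being used as the outcome, on gap sizes the documents do not give, and on no valid same-source baseline.

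This should be settled before any between-group adherence estimate is produced. Confidence is medium, because pharmacy records may already be intended for both groups; if so, stating that removes the source mismatch, though the formula, windows and baseline would still need defining.

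**What to change.** - **One measure.** In Sections 4.0, 10.0 and 12.0, define the primary adherence outcome for both groups from pharmacy records, with the same drugs, formula and windows. Proportion of days covered is one option; a single stated definition is the requirement.
- **Baseline.** Specify a pre-index baseline window in both groups, and windows matching the plan's 3-, 6- and 12-month reporting times.
- **Diary.** State that it is a navigator-group process measure and is not compared with Usual Care.
- **Usual Care data.** Replace the blanket reference to Sections 4.0 and 10.0 with a list of the items actually obtainable for that group.
- **Assistance-programme supplies.** Where retrievable, treat them the same way in both groups; otherwise report a sensitivity analysis.

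The cost is protocol and analysis wording, plus pharmacy-record extraction for the 25 navigator patients. The team must confirm that those patients' authorisation covers it, since the consent pages are not among the documents reviewed. Assistance-programme supplies may need a separate request or may not be retrievable. The remaining limitation is that fill records show possession of a drug, not that it was taken.

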| Lack of Information / Misinformation | Health literacy promotion, delivery of culturally tailored health information addressing patient and caregiver attitudes and beliefs | PN discovers patient and caregiver misperceptions about Lupus; PN provides publicly available resources from the Lupus Foundation of America website. |

| | | |
|-----------------------------|--|---|
| Poor Adherence to Treatment | Encouragement of treatment adherence through the use of medication diary / Assistance with enrolling into medication assistance programs | Patient unable to obtain medications due to lack of insurance; Assist patient with completing pharmaceutical patient assistance applications. |
| Financial Concerns | Practical support in finding community financial resources and public insurance options | Patient reports difficulty with utility bills; PN helps contact appropriate agencies for assistance. |

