5.0 Inclusion and Exclusion Criteria / Study Population

Criteria for Inclusion:

INTERVENTIONAL GROUP (n=25): 1) Self-identified Minority. 2) Patients ≥ 18 years of age as documented in the electronic medical record. 3) Meeting either American College of Rheumatology or SLICC Classification Criteria for SLE as documented in the electronic medical record (12, 13). 4) Ability to speak and understand English by self-report. 5) In the past six months having ≥ 1 missed clinic or diagnostic study/laboratory visit as documented in the electronic medical record, self-reported failure to adhere with prescribed medical therapy for SLE, or the participant is newly diagnosed with SLE. 6) In the past six months having been prescribed at least one immunosuppressive medication for SLE activity as documented in the electronic medical record regardless of whether taking the medication. 7) Have telephone access.

USUAL CARE GROUP (n=25): Meet criteria 1, 2, 3, 5, 6, 7 above for interventional group. All data from healthcare utilization and medication compliance will be collected via the CCCR biorepository request process. See data collection guidelines for this group below (Sections 12 & 13).

Criteria for Exclusion (Interventional Group only): 1) Unwilling or unable to give informed consent. 2) Being a prisoner or institutionalized individual. 3) Without telephone access. 4) Do not meet all of the inclusion criteria listed above.

Criteria for Exclusion (Usual Care Group only) 1) Do not meet usual care inclusion criteria above.

Recruitment will be enhanced by MUSC having specialized lupus clinics already in place dedicated to the care of patients with SLE.

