- 9) MacArthur Scale of Subjective Social Status (MacArthur Ladder).

Post 3, 6, & 9 Month In Person or Remote Visits:

- 1) Medication Adherence Diary review,
- 2) Steps to Care Reassessment Form,
- 3) LupusPRO survey.

Post 12-Month In Person or Remote Visit:

- 1) Medication adherence diary review,
- 2) Steps to Care Reassessment Form,
- 3) LupusPRO Survey,
- 4) Perceived Stress Survey,
- 5) Social Support Survey,
- 6) Modified Picker Survey Patient-Centered Care Questionnaire,
- 7) Experiences of Discrimination (EOD) measure,
- 8) MacArthur Scale of Subjective Social Status (MacArthur Ladder).

Monthly Phone Calls post signing of informed consent:

- 1) Steps to Care Reassessment Form

The PN will contact enrolled patients to provide appointment reminders. Contacts can be via phone, text, email, or MyChart as preferred by participant. These appointments are not only standard of care rheumatology visits but also associated to the research study in question. These contacts will be completed 15 days and 2 days prior to rheumatology clinic visit.

Additionally, the PN will call the patients one week following any changes in medications for their SLE (per primary Rheumatologist or patient reported) and will ensure patient has filled in proper

information on their Medication Adherence Diary during that contact. The PN will respond to phone calls from participating patients for health and general questions, notifying the appropriate medical provider when necessary and documenting all patient-initiated calls in the EMR. The PN will assess whether the patients' basic needs are being met (i.e. are there adequate resources for food, housing, medications, etc.) and make referrals for support services as needed (to include referrals for dietary modification, smoking cessation, exercise, obesity prevention, psychiatry, and substance abuse).

For each of these in-person visits with surveys, participants will be compensated \$10 (for a total of \$50.00 over 12 months of participation). Compensation will be delivered via ClinCard. The in-person PN visits will be planned in conjunction with scheduled outpatient clinic visits.

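### Adherence comes from pharmacy records in usual care and from a diary in the navigator group, with no rule for drug supplied outside pharmacy records

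*Combined protocol and SAP*

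**What the plan says.** Section 12.0 plans descriptive statistics "for the primary outcome measure (Medication Adherence) and all secondary outcome measures", and a propensity-weighted mixed model that compares adherence between groups. It gives no definition, metric or scoring rule for adherence.

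The source of adherence data differs by group:

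- **Usual care.** The Section 10.0 paragraph that opens "For the Usual Care Group only: As stated above, in order to properly obtain data" states: "Data on healthcare utilization and adherence to prescribed medications based on pharmacy records would be collected on the Usual Care group". Sections 5.0 and 6.0 likewise route this group's medication data through the CCCR request.
- **Navigator group.** The schedule and visit lists in Section 10.0 contain one adherence instrument, the diary. It is handed out at baseline and checked at 3, 6, 9 and 12 months ("Medication Adherence Diary review").

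Table 1 in Section 3.0 places the diary among the programme's own features: "Encouragement of treatment adherence through the use of medication diary". In the same row, the worked example of navigator help is "Patient unable to obtain medications due to lack of insurance; Assist patient with completing pharmaceutical patient assistance applications".

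Criterion 6 in Section 5.0, which applies to both groups, requires a recent immunosuppressive prescription "as documented in the electronic medical record regardless of whether taking the medication".

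Nothing states what the pharmacy records cover, or how drug obtained by another route is to be scored.

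**The concern.** A blank in a pharmacy record can mean that the drug was never obtained, or that it came by a route the record does not hold. Criterion 6 makes the first kind of patient likely in both groups. Table 1 makes the second kind a possible product of the intervention.

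The two groups are also read from different sources, and one of those sources is itself part of the intervention. The primary comparison could therefore move with how drug is supplied and how intake is recorded, and not only with whether drug is taken. Propensity weighting on baseline covariates does not correct an outcome that is measured differently by group.

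Section 12.0 intends these estimates to inform the size of a definitive randomised trial, so an error here would carry forward.

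**Working it through.** **Inputs from the plan.** 25 patients per group (Section 6.0). Two-sided alpha 0.05, power above 80% for a moderate difference in adherence rates, and precision of ±10 to 20 percentage points for proportions (Section 12.0). The plan gives no expected adherence rate and no share of patients on assistance supply.

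**The plan's own figures.** The 95% half-width for a proportion is 1.96 × √(p(1 − p)/25). This is 11.8 points at p = 0.1 and 19.6 at p = 0.5, so the stated precision is broadly reproduced. The power figure cannot be reproduced because no numerical difference is given. It is not in dispute here.

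**Assumptions.** Pharmacy records do not hold assistance supply, and a blank scores zero. The documents state neither.

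**Error in one group's mean.** Let q be the share of a group on unrecorded supply and a their true adherence. The mean is understated by at most e = q × a:

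| q | e at a = 70% | e at a = 90% |
|---|---|---|
| 5% | 3.5 points | 4.5 points |
| 10% | 7 | 9 |
| 20% (5 of 25) | 14 | 18 |
| 30% | 21 | 27 |

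The error reaches 10 points at q = 0.10/0.90 = 11% to 0.10/0.70 = 14%. These are upper limits, because they require every SLE drug to come through assistance for the whole period. A patient with one of two drugs supplied that way for half the period contributes 0.5 × 0.5 = one quarter as much.

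**Error in the comparison.** The observed difference is the true difference minus (e_N − e_U), for navigator and usual care. What matters is the gap between the two products. If the navigator group is scored from the diary, e_N = 0, leaving aside the diary's own self-report error.

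Illustration: assumed true adherence of 70% (navigator) and 30% (usual care), a 40-point difference. Shares are of the adherent patients in each group, so e = share × adherence.

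| Source | Unrecorded share, navigator / usual care | e_N, e_U (points) | Observed difference |
|---|---|---|---|
| Records in usual care only | – / 10% | 0, 3 | 43 |
| Records in usual care only | – / 20% | 0, 6 | 46 |
| Records in both | 10% / 0 | 7, 0 | 33 |
| Records in both | 20% / 0 | 14, 0 | 26 |
| Records in both | 30% / 0 | 21, 0 | 19 |
| Records in both | 20% / 20% | 14, 6 | 32 |

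The first two rows are the plan as written, and the bias favours the navigator. With no true difference and 70% adherence in both groups, a 20% share among controls would produce a spurious 0.20 × 0.70 = 14 points. The remaining rows are a design the plan does not state, and there the bias works against the navigator.

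**Effect on power, records in both groups.** For a yes/no outcome, power = Φ[(D√25 − 1.96√(2p̄(1 − p̄))) / √(p₁(1 − p₁) + p₂(1 − p₂))], where D is the observed difference. For 30% versus 70% this is Φ[(2.000 − 1.386)/0.648] = 82.8%. With 10%, 20% or 30% of adherent navigator patients unrecorded and no controls, it falls to 65.6%, 45.7% or 27.5%.

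**The case against.** The strongest reply is that no mismatch arises where the remedy acts. A reader might infer that the trial reads adherence from pharmacy records throughout, so that drug the navigator obtains is scored as not taken. The documents do not support that. The pharmacy-record sentence is confined to usual care, Section 12.0 says those patients have had no navigator contact, and the group that receives help with assistance applications has a diary. That reply stands. As written, any missed supply falls among controls and flatters the navigator; the opposite bias needs records in both groups.

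It is also fair to say that the mechanism rests on assumptions: that the records omit assistance supply, that a blank counts as zero, and that the share is material. A reader might take 3.5 to 27 points as the error in the treatment comparison. It is an upper limit for one group's mean on assumed inputs. Nor do the documents say that uninsured patients are expected to benefit most; lack of insurance is one example under one of five barriers.

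Section 12.0 says the broker will supply all data listed in Sections 4.0 and 10.0, which could be read as giving controls the same measures. But Section 10.0 limits control data to what standard care has already collected, and no diary is scheduled for controls.

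Finally, this is a non-randomised pilot with mainly descriptive analyses. That lowers the stakes but does not supply the missing rule, since the adherence comparison is planned and is meant to inform the next trial.

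**Conclusion.** The concern holds in a limited form. The primary outcome has no definition and no common source, one group's source is also an intervention component, and there is no rule for drug supplied outside pharmacy records although the navigator may move patients onto such supply. If the records omit it, the comparison is biased towards the navigator as written, and would be biased against the navigator if records alone were extended to both groups. Adopting a common source without a supply rule could therefore reverse the error and not remove it.

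The size is unknown because the share is unknown. In the illustration a 40-point difference is read as anything from 19 to 46 points. The direction depends on the source chosen, and the amount on the between-group gap in share × true adherence. The point should be settled before the control data are requested, but it does not by itself invalidate the pilot.

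**What to change.** In Sections 10 and 12:

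1. Score the primary outcome in both groups from the same source and rule. Count an SLE drug as covered by a pharmacy fill, or by assistance-programme or sample supply documented in the medical record.
2. Abstract that supply the same way in both groups, and add the supply flag and dates to the CCCR request. A prospective navigator log should not be set against a retrospective chart search in controls, because that would create a new difference in ascertainment.
3. Set drug-months with documented assistance supply of unknown dates to not assessable.
4. Report the number on assistance supply by group.
5. Keep the diary as a secondary measure in the navigator group.
6. Add a sensitivity analysis that scores unfilled orders without documented supply first as zero, then as not assessable. Do not exclude assistance-supplied patients: supply route is a post-baseline variable that the intervention changes.

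Timing is favourable. Section 6.0 identifies controls only after navigator visits finish, so the request can still carry the extra fields. It should do so then, because the data arrive de-identified and study staff may be unable to check supply later.

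The cost is some chart abstraction in both groups, some drug-months lost and one sensitivity analysis. Misclassification will remain, because shipment is not intake and controls' assistance supply may be under-documented; the report should say so.
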